16.2.4.1.6. Longitudinal Logistic Regression Model

For subjects in the All Gant exposure mITT, at each post-baseline visit including all the OLE visits, the CDR-SB value will be compared to that of the previous visit (rather than compared to highest value of previous visits), if the value of the later visit is larger than the previous one, the disease progression status is defined as 1; otherwise, the disease progression status is defined as 0. The same definition will be applied to all controls. Longitudinal logistic regression model will be applied to compare the odds of disease progression in CDR-SB between the All Gant exposure mITT and all controls. The model will include treatment group, time since baseline (continuous), interaction between the treatment group and time, and baseline EYO as the fixed

Author: [REDACTED]

Version Number:

7

Version Date:

07Dec2023

Template No.: CS_TP_BS016 Revision 6

Reference: CS_WI_BS005

Effective Date: 02Dec2019

effects, and a subject-level random intercept will also be included to account for the within-subjects correlation among the disease progression status.

Baseline CDR status will also be included in the model along with the three-way interaction between time, treatment group, and CDR status to determine if treatment before symptom onset is different from after symptom onset.

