3 STUDY PROCEDURES

3.1 Enrollment

Refer to prior protocol amendments for details associated with randomization into the double-blind period; see details in Section 3.4 of the main protocol.

After completion of the double-blind period, both the gantenerumab and solanezumab arms were analyzed and it was determined that the gantenerumab OLE period would proceed with enrollment. Any participant from either the gantenerumab or solanezumab blinded drug arms is eligible to enroll in the OLE period once confirmed as a mutation carrier, and having met the continuing eligibility requirements outlined in OLE V1 procedures (Section 3.2.1). Eligible participants were able to start treatment in the OLE period after the final analysis of the double-blind treatment period had been completed.

Figure 2 Enrollment Diagram: DIAN-TU-001 Gantenerumab Open Label Extension Period

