5.4.3. MAIN SET CONTROLS

The main set controls are defined as the external controls plus the internal set controls.

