5.4.5. CONCURRENT CONTROLS

Subjects in any control group will be identified as either concurrent or non-concurrent controls. The concurrent set of controls are defined as the internal set controls (including those in the extended set controls where applicable) and the external set controls where the point of eligibility occurs on or after the first dose of double-blind treatment in DIAN-TU-001. Based on this convention, the subject's baseline visit for internal set controls or point of eligibility for external

Author: [REDACTED]

Version Number:

7

Version Date:

07Dec2023

Template No.: CS TP BS016 Revision 6

Reference: CS WI BS005

Effective Date: 02Dec2019

set controls will have occurred within the period during which DIAN-TU-001 subjects were treated (including the gap period between double-blind and open-label treatment).

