5.4.6. CONTROLS APPLIED TO INDIVIDUAL ANALYSIS POPULATIONS

Controls will be applied to the three mITT populations as follows, with the exception that Mixed Model for Repeated Measures (MMRM) analyses will be assessed against the internal set controls (when any controls are used) and parameters which are not assessed within DIAN-OBS will be assessed against the internal set controls:

- OLE Gant mITT: Evaluated against main set controls
- OLE Gant All Gant exposure mITT: Evaluated against main set controls (as primary set of controls) and also against extended set controls (as supportive set of controls)
- All Gant exposure mITT: Evaluated against main set controls

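### The longitudinal logistic model for CDR-SB has no term for time since the previous assessment, so any group difference in visit spacing enters the treatment terms (low priority)

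*SAP*

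**What the plan says.** SAP Section 16.2.4.1.6 compares the All Gant exposure mITT with controls on a yes/no outcome at each post-baseline visit. The comparator is the preceding visit, whenever it took place: "the CDR-SB value will be compared to that of the previous visit (rather than compared to highest value of previous visits". The coding is that "if the value of the later visit is larger than the previous one, the disease progression status is defined as 1", and otherwise 0. No confirmation at a later visit is required.

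The fixed effects are listed in full: "The model will include treatment group, time since baseline (continuous), interaction between the treatment group and time, and baseline EYO as the fixed" effects. In addition, "a subject-level random intercept will also be included to account for the within-subjects correlation among the disease progression status". Baseline CDR status and a three-way interaction are added afterwards. No interval length, offset or restriction to equally spaced visits appears.

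The comparison set comes from SAP Section 5.4.6 ("All Gant exposure mITT: Evaluated against main set controls") and Section 5.4.3 ("The main set controls are defined as the external controls plus the internal set controls"). Internal controls are double-blind placebo participants who did not enter the OLE (SAP Section 5.4.2).

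On spacing, SAP Section 5.4.5 acknowledges a break in treatment, "including the gap period between double-blind and open-label treatment". Protocol Appendix 3, Section 3.1 gives the reason: participants were "able to start treatment in the OLE period after the final analysis of the double-blind treatment period had been completed".

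**The concern.** A rise in CDR-SB is more likely over two years than over one, with or without treatment. Time since baseline says where in follow-up a visit falls. It does not say how long before that visit the last assessment took place. If one group is assessed at longer intervals, it shows more rises per visit, and the model can attribute this only to group or to group by time.

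The primary CDR-SB analysis (SAP Section 16.2.3.1) works with the time elapsed between visits, and the linear mixed model uses continuous time. This model looks only at whether a rise occurred and not at the time it took. At stake is an odds ratio that could be read as supporting or contradicting slower progression when part of it reflects the visit calendar.

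**Working it through.** The plan states no power or event figure for this model, so there is nothing to reproduce. The check asks what odds ratio the coding yields with no treatment effect.

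**Formula.** With a constant yearly rise rate h, P(rise over d years) = 1 − exp(−h·d). Take h = 0.2 (assumed):
- d = 1: 0.181 (odds 0.221)
- d = 1.5: 0.259
- d = 2: 0.330

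**Who has the gap interval.** SAP Section 5.3 sets baseline for this population at the first period of gantenerumab exposure. Placebo and solanezumab participants who rolled over therefore start at OLE baseline and have no gap. Only double-blind gantenerumab participants who entered the OLE have it.

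**Share of gantenerumab intervals that are gap intervals.** Inputs: 52 double-blind gantenerumab participants (Protocol Section 3.3) and 60 to 90 of 144 carriers entering the OLE (Protocol Appendix 3, Section 4.1.2). Assumed: roll-over in proportion across arms, four annual double-blind intervals, and 2 to 3 OLE intervals each.
- 60 enter: gap intervals = 52 × 60/144 = 21.7. Total = 52×4 + 21.7 + 60×2 (or ×3) = 349.7 (409.7). Share 6.2% (5.3%).
- 90 enter: gap intervals = 52 × 90/144 = 32.5. Total = 208 + 32.5 + 90×2 (or ×3) = 420.5 (510.5). Share 7.7% (6.4%).

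The share is about 5% to 8%.

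**Null odds ratio from the gap alone**, all other intervals 1 year:
- 5% at 1.5 years: 0.181 + 0.05 × (0.259 − 0.181) = 0.185; odds 0.227; ratio to 0.221 = 1.03.
- 8% at 2 years: 0.181 + 0.08 × (0.330 − 0.181) = 0.193; odds 0.239; ratio 1.08.

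**OLE spacing.** Annual OLE visits at weeks 48, 104 and 156 give intervals of 48, 56 and 52 weeks. Rise probabilities are 0.169, 0.194 and 0.181, mean 0.181. The ratio to annual spacing is 0.9996, which is negligible.

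**Null odds ratio if some control intervals are longer**, all gantenerumab intervals 1 year:
- 25% at 2 years: 0.75 × 0.181 + 0.25 × 0.330 = 0.218; odds 0.279; 0.221/0.279 = 0.79.
- 50% at 2 years: 0.255; odds 0.343; 0.221/0.343 = 0.65.

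**Do the model's other terms absorb this?** A simulation with no treatment effect used the SAP's terms and random intercept, 92 gantenerumab, 15 internal and 80 external participants (assumed), and a joint 5% test of group and group by time. There were 100 to 200 runs per row, and the odds ratio is read at year 3. All 52 double-blind gantenerumab participants were given the gap, so its share is 52/(52×8 + 40×3) = 9.7%, above the range counted earlier.

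| External-control spacing | Gap | Null odds ratio | False positives |
|---|---|---|---|
| 1 year | 1 year | 0.98 to 1.01 | about 5% |
| 1 year | 2 years | 1.05 to 1.08 | 6% to 8% |
| 1.5 years | 1 year | 0.69 | 32% |
| 2 years | 1 year | 0.51 to 0.54 | 70% to 92% |

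The existing terms do not remove the effect. The last two rows apply longer spacing to every external control; they show the mechanism and do not estimate what will happen.

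**Offset remedy.** In the same simulation, a complementary log-log link with log(interval) as offset gave null hazard ratios of 0.98 to 1.02 and 4% to 5.5% false positives when every rise was true progression. With 10% interval-independent noise rises added (2-year control spacing, rate 0.25 per year), it over-corrected: hazard ratio 1.15, 16% false positives.

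**The case against.** The strongest reply is that large bias needs a control schedule the documents do not give. Protocol Section 3.2 describes DIAN-OBS as run under a closely similar protocol, and with annual visits throughout the simulated odds ratio is about 1. The gap effect is small and runs against gantenerumab, so it cannot create a false benefit. Missed visits are not shown to differ between groups. The retained group-by-time interaction also means that no single odds ratio fully describes the treatment effect. Finally, this is one of several supplemental CDR-SB analyses, the primary one uses elapsed time, and SAP Section 17 says this model may be run at the interim only as exploratory.

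All of that stands and limits the size. It does not remove the structural point, because a close resemblance between protocols is not a statement of equal CDR spacing, and the gap is documented.

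Three stronger readings are not supported:
- **Every gantenerumab participant has the long interval.** SAP Section 5.3 rules this out.
- **Controls include a single interval of more than four years.** That describes the extended set (SAP Section 5.4.4), which Section 5.4.6 assigns to a different population.
- **The model is shown to favour gantenerumab.** The only spacing difference the documents establish works the other way.

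**Conclusion.** The omission is real: as written, the model cannot separate a difference in visit spacing from a difference in progression. The documented gap moves the null odds ratio to about 1.03 to 1.08, against gantenerumab. This assumes a yearly rise rate of 0.2, a gap of 1.5 to 2 years and the roll-over assumptions above. If DIAN-OBS assessments are annual, the remaining bias is close to nil. If 25% to 50% of control intervals were 2 years, the null odds ratio would be about 0.79 to 0.65 in the drug's favour, but nothing in the documents shows that they are. The overall size and direction therefore cannot be fixed from the documents. The result bears on a supplemental analysis only and leaves the primary CDR-SB analysis untouched. Priority is low.

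**What to change.** In SAP Section 16.2.4.1.6, keep the logit model and its terms, and add log(years since the previous CDR-SB assessment) as an estimated covariate. Tabulate interval length by group (gantenerumab, internal controls, external controls) beside the result, so that readers can see whether spacing differed.

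The complementary log-log model with log(interval) as offset may be kept as a sensitivity analysis only. It fixes the coefficient at 1, which is wrong when some rises are rating fluctuation. Such rises do count here, because they need no confirmation and are measured against the previous visit. The simulation tested the offset and not the covariate; the reason to prefer the covariate is that its coefficient is estimated and need not be 1.

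The cost is one extra parameter and one table, from visit dates already collected. If spacing varies little within groups, the covariate will be imprecisely estimated and the treatment interval will widen. The table would show this.

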16.2.4.2. Supplemental Analysis of the CDR Global

The analysis models described in [Section 16.2.3.1](#) (Cox proportional recurrent event hazard model) and in [Section 16.2.4.1.5](#) (Logistic disease progression model) will also be applied to CDR Global for both asymptomatic and symptomatic subjects together. Models described in [Section 16.2.3.1](#) (Cox proportional recurrent event model) will also be applied separately for baseline asymptomatic and symptomatic subjects in each of the three mITT populations and all controls, with Kaplan-Meier figures presented for asymptomatic subjects.

Each subject in the OLE Gant All Gant Exposure mITT population and all controls will be categorized into 3 groups as defined in the first paragraph in [Section 16.2.4.1.1](#). The model described in [Section 16.2.3.1](#) (Cox proportional recurrent event hazard model) and in [Section 16.2.3.2](#) (Cox proportional hazard model) will be applied to the OLE Gant All Gant Exposure mITT population and all controls to compare the hazard of progression in CDR Global among the 3 subgroups.

Each subject in the All Gant Exposure mITT population and external controls will be categorized as described in the second and third paragraphs in [Section 16.2.4.1.1](#), with the analysis being applied to the primary parameter for CDR Global described in [Section 16.2.3.2](#) (Cox proportional hazards model).

[REDACTED] [REDACTED]

Author: [REDACTED]

Version Number:

7

Version Date:

07Dec2023

Template No.: CS_TP_BS016 Revision 6

Reference: CS_WI_BS005

Effective Date: 02Dec2019

16.2.4.3. Supplemental Analysis of the OLE Cognitive Composite

The supplemental analysis of the OLE Cognitive Composite will follow the logistic disease progression model in [Section 16.2.4.1.5](#) and the exponential disease progression model as described in [Section 16.2.4.1.4](#).

16.2.4.4. Supplemental Analysis of the CSF Amyloid Beta1-42/40

The supplemental analysis of the CSF Amyloid Beta1-42/40 will follow the logistic disease progression model in [Section 16.2.4.1.5](#) for the OLE Gant mITT and All Gant exposure mITT populations.

16.4. EVALUATION OF THE ASSOCIATION BETWEEN AMYLOID REDUCTION AND CLINICAL/COGNITIVE CHANGES

To evaluate if amyloid reduction is associated with clinical/cognitive benefits, the following analysis will be conducted.

1. The correlation between the change in PiB-PET SUVR and the change in clinical/cognitive

Author: [REDACTED]

Version Number:

7

Version Date:

07Dec2023

Template No.: CS TP BS016 Revision 6

Reference: CS WI BS005

Effective Date: 02Dec2019

endpoints of CDR SB and OLE Cognitive Composite will be evaluated using Spearman correlation. This correlation will be evaluated using the annual rate of change and the change from baseline to the end of OLE, respectively. The correlation will also be estimated for the subjects on double-blind gantenerumab treated group vs combined double-blind placebo and double-blind solanezumab treated group, or for subgroups defined below in item #2 (Amyloid normal group, Amyloid abnormal to normal group, and the rest). This analysis will be applied to the Gant OLE mITT and All Gant exposure mITT, respectively. Additionally, all controls will also be included to evaluate the correlation without any treatment.

2. Each subject will be categorized into 3 groups as defined in the first paragraph in [Section 16.2.4.1.1](#). The LME model will be applied to the All Gant exposure mITT population and all controls to compare the annual rate of change among the 3 subgroups for key secondary efficacy variables.

Baseline PiB PET SUVR and baseline EYO will be included as covariates in these analyses when evaluating the correlation of the annual rate of change.

For all these analyses, figures of model estimated mean over time by treatment arms or spaghetti plots of individual data over time/EYO by treatment arms will be presented as deemed necessary by Washington University team and may be included in CSR as needed.

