3. All Gant exposure mITT: Any subjects treated with Gantenerumab in either DB or OLE who meet mITT criteria using the baseline associated with the first period of Gantenerumab exposure as the baseline reference point. Refer to figure below where the data contributing to the population is highlighted in yellow (and denoted with 'Tx') any period of planned gantenerumab treatment, regardless of double-blind treatment, with controls (further described in [Section 5.4](#)) highlighted in green from both placebo double-

Author: [REDACTED]

Version Number:

7

Version Date:

[figure not shown]
07Dec2023

Template No.: CS_TP_BS016 Revision 6

Reference: CS_WI_BS005

Effective Date: 02Dec2019

blind only subjects and matched controls from DIAN-OBS.

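### SAP 16.4 leaves the total-change amyloid–clinical correlation unadjusted, which can create a spurious adverse association, most clearly in the pooled All Gant exposure mITT

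*SAP*

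**What the plan says.** Item 1 of SAP Section 16.4 relates the change in PiB-PET SUVR to the change in the clinical and cognitive "endpoints of CDR SB and OLE Cognitive Composite will be evaluated using Spearman correlation". There are two versions, annual rate and total change to the end of the OLE: "This correlation will be evaluated using the annual rate of change and the change from baseline to the end of OLE, respectively". The only covariate sentence in the section reads "Baseline PiB PET SUVR and baseline EYO will be included as covariates in these analyses when evaluating the correlation of the annual rate of change". Nothing equivalent is given for total change: no covariate, no time term, and no split by baseline CDR 0 versus CDR above 0.

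On populations: "This analysis will be applied to the Gant OLE mITT and All Gant exposure mITT, respectively" (the first is the OLE Gant mITT of Section 5.3). In the All Gant exposure mITT, Section 5.3 counts change "using the baseline associated with the first period of Gantenerumab exposure as the baseline reference point". That is the double-blind baseline for former gantenerumab participants and the OLE baseline for everyone else.

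Two further outputs are planned. One is a split: "The correlation will also be estimated for the subjects on double-blind gantenerumab treated group vs combined double-blind placebo and double-blind solanezumab treated group", or alternatively by amyloid group. The other is a comparator: "Additionally, all controls will also be included to evaluate the correlation without any treatment".

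**The concern.** Total change grows with the time over which it is counted. In a treated, progressive population, a longer interval brings both more amyloid removal and more clinical worsening. Disease stage can act the same way if later-stage participants have more amyloid to remove and also decline faster. Either path can produce an association between removal and worsening when one has no effect on the other.

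The documents support each link at least in part:

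- **Stage and decline.** Protocol Appendix 3, Section 1.4 reports no cognitive decline in asymptomatic placebo participants and substantial decline in symptomatic ones.
- **Stage and amyloid.** Protocol Section 3.1 reports that close to 30% of participants at EYO −15 to −10 had very low amyloid PET.
- **Time and removal.** Protocol Appendix 3, Section 1.4 describes greater SUVR reduction with longer exposure.

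Elsewhere the SAP handles stage: Sections 16.2.3.1 to 16.2.3.3 analyse asymptomatic and symptomatic participants separately, and Section 16.1.4.5 also runs its exposure model with disease status and EYO. Section 16.4 exists to say whether amyloid reduction accompanies clinical benefit. A spurious adverse correlation, or a real benefit hidden by one, would mislead on that question.

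**Working it through.** **Sample size and the plan's own figures.** Appendix 3, Section 4.1.2 enrols 60 to 90 with 5% annual dropout: 60 × 0.95³ = 51.4 and 90 × 0.95³ = 77.2, matching the stated 51 to 77. With SD 0.540 and one-sided 0.025, noncentral-t power at −0.473 exceeds 99.99% for both sizes. At −0.22 with N = 51 it is 81.4%. The stated figures (over 99%; more than 80%) reproduce. They are not in dispute and serve only to supply N = 51. The documents give no figure for the Spearman correlation.

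**Follow-up in the All Gant exposure mITT.** OLE dosing lasts up to 156 weeks, or 3 years (Appendix 3, Section 2.2). The double-blind period lasts 4 to 7 years (Protocol Section 6.3.5). New starters therefore have at most 3 years. Former gantenerumab participants have about 4 + 3 = 7 to 7 + 3 = 10 years, plus the gap between periods. Their share is taken as 52/144 = 36% (Protocol Section 3.3).

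**Null simulation.** N = 51, 400 runs per scenario, no effect of removal on decline. All shapes and values below are assumptions except N, the 36% share, and the 4–7 and 3-year limits.

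- Stage: EYO ~ N(0, 6), z = EYO/6.
- Baseline SUVR = 2.2 + 0.9 × [r·z + √(1 − r²)·noise], floored at 1.0, with stage–amyloid correlation r = 0, 0.3 or 0.5.
- SUVR change = −(baseline − 1.0) × (1 − e^(−0.25T)) + N(0, 0.30).
- CDR-SB change = rate × T + N(0, 0.7), rounded to 0.5, with rate = 0.9 × ln(1 + e^(1.5z)) × log-normal noise.
- T = 3 years, or uniform 1.5–3 years. In All Gant, T is uniform 1.5–3 years for everyone, and 36% have a further uniform 4–7 years.

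Entries are the mean correlation of amyloid removed with CDR-SB worsening, then the false-positive rate at nominal 5%. The sign is the reverse of a correlation on SUVR change itself.

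| Population | r | Unadjusted | PiB + EYO | PiB + EYO + time |
|---|---|---|---|---|
| OLE Gant, all 3 y | 0 | −0.01, 4% | 0.00, 4% | – |
| | 0.3 | 0.18, 28% | −0.01, 6% | – |
| | 0.5 | 0.32, 62% | 0.00, 6% | – |
| OLE Gant, 1.5–3 y | 0 | 0.03, 6% | 0.04, 5% | −0.01, 4% |
| | 0.3 | 0.17, 23% | 0.06, 7% | 0.01, 6% |
| | 0.5 | 0.28, 54% | 0.06, 9% | 0.02, 7% |
| All Gant | 0 | 0.16, 21% | 0.33, 67% | 0.05, 6% |
| | 0.3 | 0.31, 65% | 0.34, 69% | 0.06, 7% |
| | 0.5 | 0.43, 90% | 0.35, 72% | 0.07, 10% |

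**Separating the two paths.** With decline made independent of stage, follow-up length alone gave 0.26–0.28 in All Gant (48–50% false positives) but only 0.04–0.05 in OLE Gant. If fast decliners leave early, OLE Gant gave −0.08, 0.10 and 0.22 for r = 0, 0.3 and 0.5.

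**Sensitivity to inputs.** A second null simulation (60 subjects, other assumed inputs) gave 0.21–0.43 in All Gant (33–93% false positives), falling to about 0.05 only once follow-up time was included. It gave 0.00–0.31 in OLE Gant, with follow-up alone under 0.10. A follow-up-only check with 70 subjects gave 0.01–0.11 for OLE follow-up of 1.5–3 years and 0.03–0.20 for a wider 1–3 years.

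Adjusting All Gant for PiB and EYO without time does not help. At r = 0 it doubles the bias (0.16 to 0.33), because removing stage variation leaves the time link more exposed.

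**The case against.** A reader might infer that stage and follow-up alone are bound to reverse the sign in both populations, with correlations above 0.5 and near-certain significance. Inputs can be chosen that give 0.51 to 0.57, but the documents do not support that reading. The stage–amyloid correlation, the spread of OLE follow-up and the pattern of dropout are not given, and plausible values take the OLE Gant bias from 0.32 down to zero or slightly the other way.

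Further points on the other side, with what stands:

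- **End of OLE may mean Year 3.** Section 16.1.3 uses the same phrase and draws its conclusion at the Year 3 visit, and Sections 6.3 and 6.4 apply visit windows. Follow-up in the OLE Gant mITT would then be nearly constant. This stands, although the SAP's change table records early termination of the OLE, which leaves the term unsettled.
- **The split by double-blind arm.** In All Gant it separates the long- and short-follow-up groups. In the 70-subject follow-up-only check, pooled values of 0.08–0.50 fell to 0.00–0.03 and 0.01–0.12 within the two groups. This stands for follow-up. It does not address stage, and the pooled estimate is still reported.
- **Prior treatment.** Former gantenerumab participants had already lost amyloid before the OLE, which weakens any simple link between later stage and more to remove from OLE baseline. This stands.
- **Untreated controls.** Amyloid accumulates in them, so longer follow-up may link accumulation with decline, the opposite pattern. This stands, and it means the control correlation is not a clean benchmark.
- **Limited consequence.** Section 16.4 carries no decision rule and is absent from interim Table B. An adjusted annual-rate version, the item 2 LME comparison and the Cox models by amyloid group (Section 16.2.4.1.1) address the same question. This stands and limits severity.

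**Conclusion.** The gap is real: as written, the total-change correlation is unadjusted while its companion is adjusted. In the pooled All Gant exposure mITT, with no true individual-level link, it is likely to associate more removal with more CDR-SB worsening. The size is about 0.16–0.43, with a false-positive rate of about 21–93%, and unequal follow-up is a main cause. In the OLE Gant mITT the bias is about 0 to 0.32 and comes mainly from stage; follow-up alone generally adds less than about 0.10, more only if OLE follow-up is widely spread.

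These sizes rest on assumed inputs and should be read as ranges; the direction is likely, not certain. For the OLE Cognitive Composite, where decline is a lower score, the coefficient's sign reverses but its meaning does not. This is a worthwhile correction to a supportive analysis and leaves the primary PiB-PET conclusion untouched.

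**What to change.** Amend the covariate sentence in SAP Section 16.4 so that both versions are partial Spearman correlations adjusting for baseline PiB-PET SUVR and baseline EYO, with the total-change version also adjusting for the years between the baseline and the last measurement used. Follow-up time is essential, because PiB and EYO alone do not repair the All Gant version. The alternative is to drop the total-change version and keep the adjusted annual rate.

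The same edit should say which visit counts as the end of the OLE after early termination, and what takes its place for controls, who have no OLE. Even with all three covariates, the All Gant simulations left a small residue (0.05–0.07, false-positive rate about 6–10%), so a total-change result there is best reported as descriptive. The cost is a sentence or two of SAP text and no new data.
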